### **10.2.2 Reporting of Serious Adverse Events**

All SAEs, whether or not thought related to the investigational product, must be reported by the Investigator or designee (by telephone, fax or email) [REDACTED] within 24 hours of the Investigator becoming aware of the event. The Investigator or responsible clinical site staff will complete and submit the Serious Adverse Event report form and then enter all adverse events into the eCRF.

Serious adverse event reports should be sent to:

Following receipt of the SAE report, the Safety group will review the report and contact the Investigator to request additional information or for data clarification. Redacted medical records supporting the event should be submitted as they become available. For all SAEs occurring during the study, the Investigator must submit follow-up reports [REDACTED] [REDACTED] regarding the participant's subsequent course until the SAE has resolved, reached a stable outcome, or is no longer clinically significant. The timelines and procedure for follow-up reports are the same as those for the initial report. The submitted reports must be retained by the site.

### 10.3 Stopping Rules and Dose Limiting Toxicity (DLT)

The DLT observation period to determine the safety of a dose is defined as starting with administration of the first dose of AT-1501 to the first participant in a cohort through the administration of the second dose of AT-1501 in the 6th participant in that cohort. This will repeat for each dose level.

Any of the below outlined events occurring during the DLT observation period and considered to be **at least possibly related** to AT-1501 will qualify as a DLT.

A DLT is further defined as:

1. An event which meets the laboratory criteria for potential Drug Induced Liver Injury (DILI) or “Hy’s Law” defined as:
  - An elevated alanine transaminase (ALT) or aspartate transaminase (AST) lab value that is greater than or equal to three time (3x) the upper limit of normal (ULN) **WITH**
  - An elevated total bilirubin lab value that is greater than or equal to two times (2x) ULN without findings of cholestasis, **AND**
  - At the same time, an alkaline phosphatase (ALP) lab value that is less than 2x ULN
2. Any study drug related Grade 3 or greater toxicity with the exception of a Grade 3 or greater laboratory abnormality that is considered clinically insignificant and does not meet the criteria of an adverse event.
3. Any study drug related serious adverse event, regardless of severity.
4. A second occurrence of a similar Grade 2 or greater study drug related event within a cohort. That is, if two or more participants in a cohort experience a similar drug related AE greater than or equal to Grade 2 toxicity, a DLT has been met.

If any DLT criteria are met, further enrollment will be paused and the appropriate DLT data will be reviewed by Anelixis to determine an immediate course of action to be taken. If there are two or more occurrences of a DLT, the study may be temporarily halted until a more thorough safety review is undertaken.

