### 5.3 Dose Escalation

Participants will be enrolled into 1 of 4 sequentially enrolling cohorts (1.0 mg/kg; 2.0 mg/kg; 4.0 mg/kg; and 8.0 mg/kg). Nine participants will be enrolled into each of the 1.0 mg/kg and 2.0 mg/kg cohorts and 18 participants will be enrolled into each of the 4.0 mg/kg and 8.0 mg/kg cohorts. Dose escalation decisions will be made by Anelixis with input from the DMC (See 5.4 Data Monitoring Committee) and Investigators. After the decision has been made to continue dosing a cohort the next dose cohort will be allowed to start, once the last participant enrolled to the current cohort has received their first dose. This process will be followed for each cohort.

The planned dose escalation scheme may be amended based on review of the emerging data. Additional cohorts may be added, and smaller cohort sizes may be implemented based on safety data and [REDACTED].

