## 5.4 Data Monitoring Committee

A DMC will be established and will be comprised of 2 physicians (with ALS experience and no other involvement in the trial) and a statistician.

The committee will meet following the administration of 6 doses to a minimum of 33% of participants, in each cohort. The meetings for dosing cohorts 1 and 2 will be held after 3 participants have received 6 doses, for a total of 18 doses. The meetings for dosing cohorts 3 and 4 will be held after 6 participants have received 6 doses, for a total of 36 doses. The review will include all the available safety and laboratory data, including but not limited to platelet levels and coagulation data. [REDACTED] data may be reviewed depending on data availability. The committee may recommend a revision of the dose escalation scheme based on review of the emerging data.

The DMC is responsible for making a recommendation to continue enrolling at the current concentration, escalate to the next planned dose, recommend changes in study conduct, or stop further dosing in the study. Specific responsibilities of the DMC are detailed in the DMC Charter including meeting schedules, documentation requirements, and data review. The DMC may meet on an ad hoc basis should an emergent safety issue be identified (see [Section 10.3](#)).

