## 6.6 Study Drug Discontinuation

Participants may be discontinued from receiving study drug for any of the following reasons:

- Lack of cooperation with study requirements;

- Intercurrent illness, that in the opinion of the Investigator, would unreasonably increase the risks of the study procedures, or otherwise compromise the safety of the participant or the integrity of study results;
- Participant refuses further treatment with AT-1501;
- Actions taken to control the -spread of COVID-19 (e.g. no access to study drug)
- Active COVID-19 infection
- Participant Withdraws consent to the trial;
- Stopping rules are met;
- At the direction of Anelixis;
- At the direction of the Investigator.

The effects of AT-1501 have not been studied in patients that have been diagnosed with COVID-19. It is unknown whether taking the investigational drug will increase or decrease the risk of getting COVID-19 or the effect it may have on the clinical course of a participant who develops COVID-19. Potential participants for the study will be tested for COVID-19 prior to entering the study. If a participant tests positive they will not be allowed to participate in the study. If a participant is diagnosed with COVID-19 while receiving treatment in this study, the administration of the investigational drug will be stopped, and appropriate medical care and follow-up will be done. The participant will continue to be monitored for safety.

All participants that withdraw from treatment with AT-1501 for any reason should continue to be followed until the end of study.

If at any time during the study a participant experiences an adverse event the Investigator believes is severe enough to preclude further AT-1501 administration or the stopping rules are met the participant will be discontinued from study drug treatment and will receive medical treatment as determined by the Investigator. The participant will be followed until the event resolves or until the Investigator determines the AE has reached a stable outcome or is no longer clinically significant. Regardless, each participant will be followed for safety for at least 4 weeks from the last AT-1501 infusion. A final visit will be completed according to the end-of-study evaluation (Section 7.6).

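### As literally written, the protocol's only event-triggered enrolment pause lapses in each cohort at the 6th participant's second dose, so a later related SAE, Grade 3+ toxicity or Hy's Law case triggers no required pause

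*Protocol*

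**What the plan says.** Protocol 10.3 opens the DLT observation period at the first dose in a cohort and runs it "through the administration of the second dose of AT-1501 in the 6th participant in that cohort". The synopsis and section 5.1 give the same definition. A DLT must fall inside that period and be at least possibly related: "Any of the below outlined events occurring during the DLT observation period". The four criteria are a Hy's Law pattern, a related Grade 3 or higher toxicity (with an exception for clinically insignificant laboratory values), any related SAE, and a second similar related event of Grade 2 or higher in the cohort.

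The consequence is: "If any DLT criteria are met, further enrollment will be paused and the appropriate DLT data will be reviewed by Anelixis". Two or more DLTs may lead to a temporary halt.

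Other provisions bear on later events:

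- **Section 6.6** stops drug in a participant, at any point in the study, if the investigator judges an adverse event severe enough "or the stopping rules are met the participant will be discontinued from study drug treatment".
- **Section 10.2.2** requires SAE reports "within 24 hours of the Investigator becoming aware of the event", followed by Safety group review.
- **Section 5.4** schedules one DMC review per cohort by dose count. For the larger cohorts: "The meetings for dosing cohorts 3 and 4 will be held after 6 participants have received 6 doses, for a total of 36 doses". It adds: "The DMC may meet on an ad hoc basis should an emergent safety issue be identified", with a cross-reference to 10.3.
- **Section 13.1** lets the sponsor terminate the study at any time.

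The SAP contains no stopping rule.

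**The concern.** The primary objective is the safety of multiple doses, and the Phase 1 study described in section 3.4 gave single doses only. Section 10.3 is headed as the stopping rules, yet its window need contain no more than two doses in each of the first six participants. If the rule ends there, the only predefined link between a serious related event and a pause is gone before most repeat dosing has been observed.

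The window does not control escalation either. The next cohort waits for DMC review and a decision to continue ("After the decision has been made to continue dosing a cohort the next dose cohort will be allowed to start"), so ending the pause with the window buys nothing that the documents state. At stake is whether, after a serious related event, new participants keep starting at the same dose until someone chooses to intervene or the scheduled review arrives.

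**Working it through.** **The text.** The 10.3 definition limits DLTs to the window, and both consequences in 10.3 depend on a DLT. The other provisions compare as follows:

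- 24-hour SAE reporting and Safety group review are mandatory, but specify no pause. A non-serious Grade 3 event or a Hy's Law laboratory pattern need not enter that route.
- The scheduled DMC review is mandatory and can recommend stopping, but a dose count triggers it, not an event.
- The ad hoc DMC meeting and sponsor termination are discretionary.
- Section 6.6 acts on one participant, not the cohort.

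None of these ties a qualifying event to a cohort-level pause.

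**Inputs.** Cohorts of 9, 9, 18 and 18; six doses at 14-day intervals (5.1); DMC review in cohorts 3 and 4 after six participants have six doses (5.4); about 18 months in total (synopsis, 5.7). The plan's own figures reproduce: 9 + 9 + 18 + 18 = 54 participants; 3 × 6 = 18 and 6 × 6 = 36 doses at the DMC reviews. Planned infusions are 54 × 6 = 324, or 108 in an 18-person cohort.

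**Assumption.** No accrual rate is given, so participants are taken to start evenly, g days apart, with no missed doses. Day 0 is the cohort's first dose. Participant i (0 to n − 1) is dosed on days gi + 14k, k = 0 to 5.

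- Window closes: 5g + 14.
- Scheduled DMC review in cohorts 3 and 4, at the earliest: 5g + 70. The gap is 56 days for any g.
- An enrolment pause after closure can hold back only participants with gi > 5g + 14, six infusions each.

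**Weekly enrolment, 18-person cohort (g = 7).** The window closes on day 49. The earliest fifth dose is day 56 and the earliest sixth is day 70. Doses inside the window number 4+4+3+3+2+2+1+1 = 20, leaving 88. Participants i = 8 to 17 start later: 10 people, 60/108 = 56% of infusions. The other 88 − 60 = 28 belong to people already started. Eight of the ten start by the DMC review point (day 105), the eighth on that day. After the 18th first dose (day 119), 30 of 108 infusions (28%) remain, and an enrolment pause in that cohort cannot affect them.

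| Spacing g (days) | Window closes (day) | Start after closure, of 18 | Infusions, of 108 |
|---|---|---|---|
| 0 or 1 | 14 or 19 | 0 | 0 (0%) |
| 2 | 24 | 5 | 30 (28%) |
| 5 | 39 | 10 | 60 (56%) |
| 7 | 49 | 10 | 60 (56%) |
| 10 | 64 | 11 | 66 (61%) |
| 14 | 84 | 11 | 66 (61%) |

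The window closes before any fifth dose when 5g + 14 < 56, that is g < 8.4 days.

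**9-person cohorts at g = 7.** One participant starts late: 6/54 = 11%. The DMC point is 2g + 70 = day 84, a gap of 84 − 49 = 35 days. Over the trial: (2 × 60 + 2 × 6)/324 = 132/324 = 41%.

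**Plausibility of g.** With 28 days of screening, immediate DMC decisions and no replacements, trial length is 28 + 2·max(2g+70, 8g) + max(5g+70, 17g) + 17g + 100. At g = 7 this is 28 + 168 + 119 + 119 + 100 = 534 days, or 17.5 months, consistent with 18. Spacings of 2 and 14 days give 12.8 and 27.2 months, so the long end fits poorly.

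**Frequency of pauses if the rule is extended.** Assume independent infusions with a 1% risk each of a qualifying related event, at g = 7. The chance of at least one in an 18-person cohort is 1 − 0.99^20 = 18% with the present window and 1 − 0.99^108 = 66% with all dosing covered. At 0.5% it goes from 9.5% to 42%; at 2%, from 33% to 89%. Over the trial at 1%, covered infusions rise from 4 × 20 = 80 to 324, and the chance from 55% to 96%. The extended figures are upper limits, since a late event may find no enrolment left to pause.

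**The case against.** The strongest reply is that 10.3 was meant to stay live. Its action sentence speaks of the criteria being met, 6.6 invokes the stopping rules throughout the study, and 5.4 points to 10.3 for ad hoc DMC meetings. This may well be the intent, and if so the fault is drafting. It does not settle the matter: the sentence before the criteria confines DLTs to the window, and 10.3 never mentions the DMC. The 6.6 wording is also weak evidence either way, because 10.3 sets no participant-level action even inside the window.

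A second reply is that a bounded window to judge a dose level, followed by DMC review, is a recognised design, and 10.3 states that purpose. That stands for counting DLTs. It does not explain why the pause should end with the counting.

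Third, the remaining oversight is substantial. A reader might infer that cohorts go unmonitored after the window, or that its closing lets escalation proceed on thin evidence. The documents support neither. SAE reporting and the scheduled DMC review are mandatory, platelets and coagulation are tested before each dose (7.4), and escalation waits for the DMC. Nor do the documents point to a raised thromboembolic risk: section 3.2 describes structural changes meant to lower it and supportive preclinical data. The DMC Charter may also set triggers that the protocol does not.

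Finally, an extended rule could pause often, because a possible relationship under 10.1.4 includes events that concurrent disease could explain, which is likely in ALS. That stands, and it shapes the fix.

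**Conclusion.** The point holds for the literal text: the event-triggered enrolment pause and sponsor review lapse at the 6th participant's second dose, and neither document supplies another event-triggered cohort-level action. What is lost is that trigger, not safety oversight as a whole. The gap in wording does not depend on accrual; its size does. At one enrolment per week, 10 of 18 participants in each of the two highest-dose cohorts start after the window closes.

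The 56% should not be read as the share of unprotected infusions. It is the most that a pause could have held back, if the event came just after closure and the pause were never lifted; with spacing of 0 to 1 day it is 0%. The change should be made because it is inexpensive and bears on the primary objective. Confidence is medium, since the intent is unclear and the Charter was not seen.

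**What to change.** Keep the present window for DLT counting and for criterion 4. In 10.3, mirrored in the synopsis and 5.1, state that an event meeting criteria 1 to 3 at any time up to 4 weeks after the last participant's last dose in the cohort:

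- triggers prompt sponsor review with DMC notification, including whether participants already enrolled continue dosing; and
- pauses further enrolment in any open cohort until that review is complete.

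The review then still has effect in a fully enrolled cohort and in the final 8 mg/kg cohort. In 6.6, name which 10.3 criteria require the affected participant to stop drug. Align the DMC Charter if needed.

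The cost is protocol wording and more short enrolment pauses, possibly many more, as the calculation shows. Tying each pause to completion of the review limits its length. No visits, participants or data are added, because 10.1.1 already collects all adverse events to the final visit.

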## **11 STATISTICAL EVALUATION**

### **11.1 Justification of Sample Size**

Approximately 54 adults with ALS will be enrolled into the study. All participants will receive AT-1501. The sample size for this study is not based on formal statistical computation. The number of participants by dose level has been chosen in order to examine initial safety at lower doses and to examine [REDACTED] endpoints at higher doses with a sufficient number of participants. The sample size may increase in order to allow for replacement of patients who are withdrawn or withdraw prior to receiving at least 4 infusions of AT-1501.

### **11.2 Definition of Study Analysis Sets**

#### **11.2.1 Safety Analysis Set**

All enrolled participants who receive at least one dose of study medication will be included in the Safety Analysis Set (SAS).

#### **11.2.2 Full Analysis Set**

All enrolled participants who receive at least one dose of study medication and at least one post-baseline measurement will be included in the Full Analysis Set (FAS).

#### **11.2.3 Evaluable Analysis Set**

The Evaluable Analysis Set (EAS) will include all treated participants who have no important protocol deviations likely to seriously affect the primary outcome of the study.

### **11.3 Statistical Analysis**

A detailed description of the planned statistical methods will be documented in a statistical analysis plan (SAP). All statistical analyses will be performed using SAS® software ver. 9.4 or higher.

All continuous variables will be summarized by treatment and visit (as applicable) using descriptive statistics (number of observations [n], mean, median, standard deviation, minimum and maximum). All categorical variables will be summarized by treatment, visit and time point (as applicable) using frequency counts and percentages.

#### **11.3.1 Study Baseline**

Baseline will be defined as the last available observation prior to administration of the dose.

#### **11.3.2 Disposition of Participants**

Participant enrollment, inclusion into each study population, discontinuation and withdrawal from the study will be summarized.

### 11.3.3 Demography and Baseline Characteristics

Participant characteristics such as gender, age, race and ethnicity as well as important disease characteristics will be described using summary statistics.

### 11.3.4 Safety

Safety will be summarized by dose level. Adverse events will be mapped by system organ class (SOC) and preferred term using the MedDRA dictionary and will be graded and recorded according to the CTCAE. Safety analyses may include the following:

- Summary of adverse events
- Summary of serious adverse events
- Summary of adverse events by CTCAE grade
- Summary of adverse events related to investigational product
- Summary of adverse events by CTCAE grade and relationship to investigational product
- Laboratory changes from baseline
- Vital signs changes from baseline
- ECG changes from baseline
- C-SSRS changes from baseline
- Percentage of participants to complete all 6 doses

### 11.3.6 Medical History

Medical history and information about underlying disease for all participants will be listed.

### 11.3.7 Prior and Concomitant Medications

Prior medications are those medications taken before the date of the first dose of investigational product. Concomitant medications are those medications taken on or after the date of the dose of investigational product. All prior and concomitant medications will be summarized by dose level.

#### **11.4 Handling of Missing Data**

Data will be analyzed as collected. Missing data will not be imputed.

#### **11.5 Interim Analysis**

No interim analysis is planned for this study.

[REDACTED]

### **12 DATA MANAGEMENT**

#### **12.1 Participant Data Protection**

Participant number, year of birth, race and gender will identify the study subjects in the eCRFs.

The Investigator is responsible for keeping a list of all consented participants including participant numbers, full names and date of birth. In addition, the Investigator will prepare a list of participants who were screened for participation in the trial but were not treated and the reason for non-eligibility.

The participants will be informed in writing that the results will be stored and analyzed in a computer according to national laws, as applicable, and that participant confidentiality will be maintained.

The participants will also be informed in writing about the need for source data verification (SDV), audits and inspections. The audit/inspection and SDV will be performed by at least one of the following parties: authorized representatives of Anelixis Therapeutics, Inc., authorized monitors, clinical site IRBs or regulatory authorities. In these cases, the relevant part of the participant's notes will be required and reviewed.

#### **12.2 Data Handling**

The Investigator or his/her designee will document all data obtained during the study using the electronic data capture system provided by Anelixis Therapeutics, Inc. or designee. This also applies to data for those participants who, after having consented to participate, underwent

baseline examinations required for inclusion into the trial, but who were not included in the study.

In the process of ensuring data completeness and accuracy, a 100% SDV will be performed. The Investigator will complete and maintain source documents for each participant participating in the study. Source data is the first place the data is recorded, regardless of where this is. AEs and SAEs together with visit dates and information about the disposition for each participant should be recorded in the participant medical chart/notes.

For all participants, Anelixis Therapeutics, Inc. or its designee will validate the completed eCRFs. The Investigator will retain a copy of the printed eCRF, or equivalent. If data management detects eCRFs with missing or inconsistent data, queries will be sent into the system for correction by the Investigator. The Investigator will also receive data queries, which might be generated during the computerized data validation process.

Source data, source documents, CRFs, protocol and amendments, drug accountability forms, correspondence, participant identification list, informed consent forms, and other essential documents must be retained for at least 2 years after the last approval of a marketing application in an ICH region and until there are no pending or contemplated marketing applications in an ICH region, or at least 2 years have elapsed since the formal discontinuation of clinical development of the investigational product. It is the responsibility of the Sponsor to inform the Investigator/institution as to when these documents no longer need to be retained consistent with regulations under ICH GCP.

Anelixis Therapeutics, Inc. or its designee will be responsible for data processing and data control. Participant data will be entered into the clinical database continuously by the clinical site. All original documents and CRFs will be retained in the archives of Anelixis Therapeutics, Inc. as long as the product under investigation remains available for human use.

